### **1.4. Exploratory Analyses**

For the exploratory analysis, patients who enrolled in the VBHI program in the first 9 months from study start will have their symptoms (depression score reduction, depression remission, suicidal ideation score reduction, anxiety score reduction) and health outcomes (BMI, LDL, and HbA1c) assessed at 3, 6, 9, and 12-months.

- Symptom improvement
  - Depression: Percent of patients with a 50% reduction of PHQ-9 score from initial assessment
  - Depression Remission: Percent of patients with a PHQ-9 score <5 (for 2 consecutive months upon graduation)
  - Suicidal ideation: Percent of patients with a PHQ-9, Question #9=0 or C-SSRS negative upon graduation
  - Anxiety: Percent of patients with a 50% reduction of GAD-7 score among patients with an initial score of > 10
- Health Outcomes
  - Reduction in BMI among patients with an initial BMI  $\geq 25.0$
  - Reduction in HbA1c among diabetic patients with an initial A1c  $\geq 9$
  - Reduction in LDL cholesterol level among patients with an initial LDL  $\geq 160$

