#### 5.1.2. Rates and Variable Descriptions

- a. Demographic characteristics (age, race, gender, insurance plan)
- b. Charlson comorbidity index score

If we determine that we can identify hospital and primary care visits through claims data, we will use that as a source over using just Atrium Health encounters for the utilization rates as specified below.

- c. Patient-centric defined 90-day utilization rate. This is a utilization rate among patients with an ED, inpatient, or observation encounter to any Atrium Health facility ( $\leq 90$  days after the primary care visit).
- d. The 90-day primary care utilization rate. This is a utilization rate among patients with a primary care encounter ( $\leq 90$  days after the primary care visit).
- e. Primary care visit
  - i. At least one CPT code for preventative or outpatient visit
- f. Pharmacy related 90-day total cost of care. The pharmacy total cost of care is defined as the summation of all pharmacy paid claims within 90 days of the primary care visit among patients with pharmacy claim data ( $\leq 90$  days after the primary care visit).

Symptom and health outcomes are assessed at 3, 6, 9, and 12-months among patients who enrolled in the VBHI program.

- g. Asses symptom improvement for depression
  - i. Pre- PHQ-9 score from primary care visit
  - ii. Post- PHQ-9 score
- h. Primary care visit diagnoses (primary or secondary billed diagnoses)
  - i. substance use disorder
  - ii. depression/dysthymia
  - iii. anxiety
- i. Anxiety
  - i. Pre- GAD-7 score from initial enrollment
  - ii. Post- GAD-7 score

- j. Suicidal ideation
  - i. Pre- PHQ-9, Q9 score from primary care visit
  - ii. Post- PHQ-9, Q9 score
- k. Remission of depressive symptoms
  - i. PHQ-9 less than 5 in 2 consecutive months
- l. BMI
  - i. Pre- BMI level from primary care visit
  - ii. Post- BMI level
- m. HbA1c among diabetic patients
  - i. Pre- A1c level from primary care visit
  - ii. Post- A1c level
- n. LDL cholesterol level
  - i. Pre- LDL level from primary care visit
  - ii. Post- LDL level
- o. Hunger vital signs – reported upon enrollment
  - i. Within the past 12 months, we worried whether our food would run out before we got the money to buy more?
  - ii. Within the past 12 months the food we bought just didn't last and we didn't have the money to get more?
- p. Home – reported upon enrollment
  - i. What is your housing situation today?
  - ii. Are you worried about losing your house?

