In addition, per-protocol analyses of the primary and secondary outcomes will be performed to evaluate the effect of VBHI program participation, in contrast to the ITT analysis evaluating the effectiveness of referral to the program. The per-protocol analyses will include only subjects who received and adhered to the treatment (VBHI program or usual care) assigned to their clinic. The analyses will be similar to those described above for ITT, except the primary predictor is an indicator for treatment (VBHI program or usual care) received rather than treatment assigned. To help address confounding due to incomplete adherence, the per-protocol analyses will adjust for pre-randomization and post-randomization factors that predict adherence. To identify such factors, a separate, multivariable logistic regression analysis will be performed on the full dataset with adherence (yes/no) as the dependent variable.

Exploratory analyses will evaluate baseline to 3-, 6-, 9-, and 12-month changes in symptom improvement and health outcomes using generalized linear mixed models with a logit link, where the dependent variable is binary (e.g., 50% reduction of PHQ-9 score from initial assessment (yes/no)). Random effect terms in the model will account for within-practice clustering and within-patient correlation. Fixed effects will be the treatment group indicator, time indicator, and interaction between treatment group and time.

All tests will be two-sided and the data will be analyzed using SAS Enterprise Guide 7.1 (SAS Institute Inc., Cary, NC, USA).

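### BMI, HbA1c and LDL are put into a yes/no logit model with no stated size of reduction; analysing the recorded levels as continuous values would keep at least 36% of the information that is lost

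*Combined protocol and SAP*

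**What the plan says.** Section 6.2 covers both kinds of exploratory outcome in one sentence. On scope it says: "Exploratory analyses will evaluate baseline to 3-, 6-, 9-, and 12-month changes in symptom improvement and health outcomes". For the method it names a single approach that serves every one of these outcomes, namely "using generalized linear mixed models with a logit link, where the dependent variable is binary". Its one example is the 50% fall in PHQ-9. No other model is given for BMI, HbA1c or LDL.

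Section 1.4 defines the depression response by a threshold: "Percent of patients with a 50% reduction of PHQ-9 score from initial assessment". Remission, suicidal ideation and anxiety also have thresholds. The health outcomes do not. They read "Reduction in BMI among patients with an initial BMI" of 25.0 or more, "Reduction in HbA1c among diabetic patients with an initial A1c" of 9 or more, and "Reduction in LDL cholesterol level among patients with an initial LDL" of 160 or more. The Protocol Summary lists the same three, also without a size of reduction.

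Section 5.1.2 (items l to n) lists a pre and a post level for each measure, for example "Pre- A1c level from primary care visit". On the population it says: "Symptom and health outcomes are assessed at 3, 6, 9, and 12-months among patients who enrolled in the VBHI program". The model in section 6.2 nevertheless has a treatment group indicator and its interaction with time.

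**The concern.** A binary model needs a rule that turns each patient's change into yes or no. With no threshold, the rule that the text most naturally yields is any fall at all. An LDL fall of 1 point and one of 60 points then score the same, and the size of change, which section 5.1.2 already records, plays no part in the analysis.

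Precision is lost for no gain. In addition, HbA1c and LDL are examined only in patients with high starting values, in whom a later reading tends to be lower with no programme effect. A large percentage reduced could be read as benefit.

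**Working it through.** The plan gives no sample size, expected proportion, SD or retest correlation for these outcomes, so there is no figure to reproduce.

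**1. Information kept by a yes/no cut.** If a normally distributed change is cut so that a proportion p counts as reduced, the share of information kept is φ(c)² / [p(1 − p)], where c is the normal quantile of p and φ the normal density.

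| p reduced | c | φ(c) | Kept | Lost | Patients needed, ratio |
|---|---|---|---|---|---|
| 0.50 | 0 | 0.399 | 2/π = 0.637 | 36% | 1.57 |
| 0.69 | 0.496 | 0.353 | 0.582 | 42% | 1.72 |
| 0.77 | 0.739 | 0.304 | 0.521 | 48% | 1.92 |

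The 50:50 row is the smallest possible loss. The further the split is from one half, the more is lost.

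**2. How many patients fall by chance.** Assume that levels are stable over time and bivariate normal with retest correlation r, and that patients are selected at z ≥ zc, where z is the standardised baseline. With no effect, P(fall) is the mean of Φ(z·√[(1 − r)/(1 + r)]) over the selected patients. The multiplier is 0.420 for r = 0.7 and 0.333 for r = 0.8. The means and SDs below are my assumptions.

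| Outcome | Assumed mean, SD | zc | P(fall), r = 0.8 | P(fall), r = 0.7 |
|---|---|---|---|---|
| HbA1c ≥ 9 | 7.5, 1.6 | 1.5/1.6 = 0.94 | 69% | 73% |
| LDL ≥ 160 | 115, 35 | 45/35 = 1.29 | 72% | 77% |

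The lowest and highest of these, 69% and 77%, give the 42% and 48% losses in step 1. Allowing for the truncated baseline changes those losses by less than one percentage point.

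**3. Wider assumptions, with BMI.** The loss here is against a continuous change score.

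| Outcome | Entry value, SDs from mean | r | Fall by chance | Lost |
|---|---|---|---|---|
| BMI ≥ 25 | −1 to 0 | 0.90 to 0.98 | 51 to 57% | 36 to 37% |
| HbA1c ≥ 9 | 0.5 to 1.3 | 0.50 to 0.85 | 63 to 84% | 39 to 56% |
| LDL ≥ 160 | 1.0 to 1.8 | 0.50 to 0.85 | 67 to 89% | 41 to 64% |

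Against a baseline-adjusted continuous model the losses are slightly larger: 37 to 39%, 40 to 58% and 41 to 66%.

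**4. The same loss as sample size (illustration only).** Take two independent groups, a shift of 0.3 SD, two-sided 5% and 80% power. The continuous analysis needs 2 × (1.96 + 0.84)² / 0.3² ≈ 175 per group. The yes/no version needs 278 if 50% fall by chance and 327 if 70% do, which is 1.59 and 1.87 times as many. With 175 per group its power is 60% and 54%.

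**5. Does a continuous outcome remove regression to the mean?** No. The expected chance fall in the selected patients is (1 − r) × SD × φ(zc)/[1 − Φ(zc)]. For LDL the last ratio is about 1.76, so the mean falls by 0.2 × 35 × 1.76 ≈ 12 points (r = 0.8) to 0.3 × 35 × 1.76 ≈ 18 points (r = 0.7) with no effect.

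**The case against.** The strongest reply is that the plan never says any reduction. Its only binary example is PHQ-9, and the health outcomes are not worded as percentages of patients, as the symptom outcomes are. A threshold or a continuous analysis may have been intended and left unwritten. That stands as a limit on the claim: any reduction is the natural reading, not a stated rule. It does not remove the point, because section 6.2 gives these outcomes no other model, and the remedy is to write the intention down.

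Three stronger readings are tempting and are not supported.

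- A reader might infer that most patients in all three groups will fall by chance. For HbA1c and LDL the direction is robust over the ranges tried, but the percentages rest on assumed distributions. For BMI the figure is close to one half.
- A reader might infer that a continuous analysis cures regression to the mean. It does not, as step 5 shows, and without a comparator a baseline covariate does not remove it either. PHQ-9 and GAD-7 are also assessed in patients with high starting scores. The case for changing the model therefore rests on precision.
- A reader might infer that the subgroups are too small to bear the loss. The documents give no counts for them.

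It is also fair to say that responder analyses are common and that nothing confirmatory depends on these outcomes. That limits the importance of the point. It is no argument for discarding levels that will be recorded anyway.

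**Conclusion.** The point holds as a matter of precision and definition. As written, BMI, HbA1c and LDL go into a binary model with no size of reduction stated. For a normal change score this loses at least 36% of the information. For HbA1c and LDL the loss is about 42 to 48% under the assumed means, SDs and retest correlations of 0.7 to 0.8, and 39 to 64% over the wider ranges. For BMI it stays near the 36% minimum.

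Regression to the mean is a matter of interpretation under either analysis. It can be separated from programme effect only with usual-care patients, and on this the plan conflicts with itself: the Protocol Summary and sections 1.4 and 5.1.2 restrict these outcomes to enrollees, while section 6.2 fits treatment-group and group-by-time terms that cannot be estimated in enrollees alone.

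The consequence is minor. The outcomes are exploratory, and no primary or secondary conclusion depends on them.

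**What to change.** Amend section 6.2 as follows.

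1. Analyse BMI, HbA1c and LDL as continuous values in a linear mixed model with random effects for practice and patient, and with time and baseline value as fixed effects. Report mean change at 3, 6, 9 and 12 months with 95% confidence intervals.
2. Keep the logit model for outcomes with a stated threshold. Make any yes/no version of BMI, HbA1c or LDL supportive, with its cut-off written down before analysis.
3. State that change after selection on a high baseline includes regression to the mean, and that neither the continuous model nor baseline adjustment removes it without usual-care patients.
4. Reconcile the population with the model. Either include usual-care patients for whom these levels exist and keep the treatment-group and group-by-time terms, or stay with enrollees, drop those terms and describe the results as uncontrolled change.

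Items 1 to 3 cost a few sentences: the levels are already listed in section 5.1.2, the same software serves, and section 6.2 already uses a linear mixed model for cost. Item 4 costs wording only if the analysis stays with enrollees. Including usual-care patients would mean retrieving their levels as well.

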Study Objectives	
The primary objective is to evaluate the effectiveness of the virtual behavioral health integration (VBHI) program compared to usual care, on reducing the total cost of care reimbursed from Medicare and value-based contracts within 90 days of a patient’s primary care visit.
 
Secondary objectives of the evaluation include:
 
 
• Compare demographics, Charlson comorbidity index, and social determinants of health among patients (hunger vital signs, home, education, employment, social and emotional health) between the two arms of the study
 
• Compare the 90-day acute care utilization rate after the index primary care visits
 
• Compare the 90-day primary care utilization rate after the index primary care visit
 
• Compare the pharmacy related 90-day total cost of care after the index primary care visit
 
• Stratify and report objectives by index primary care visit diagnoses (substance use disorder, depression/dysthymia, anxiety)
 
 
Exploratory analyses among patients who enrolled in the VBHI program. A subgroup of patients whose index primary care visit is within 9 months of the study start. Assessment at 3, 6, 9, and 12-months
 
 
• Symptom improvement 
 
○ Depression: 50% reduction of PHQ-9 score from initial assessment
 
○ Depression Remission: Percent of PHQ-9 scores <5 (for 2 consecutive months upon graduation)
 
○ Suicidal ideation: Percent of PHQ-9, Question #9=0 or C-SSRS negative upon graduation
 
○ Anxiety: GAD-7, 50% reduction from initial assessment
 
 
 
• Health Outcomes 
 
○ Reduction in BMI among patients with an initial BMI <math>\geq 25.0</math>
 
○ Reduction in HbA1c among diabetic patients with an initial A1c <math>\geq 9</math>
 
○ Reduction in LDL cholesterol level among patients with an initial LDL <math>\geq 160</math>
 
 
 

Inclusion Criteria	
Inclusion criteria:
 
 
• 18 years of age or older
 
• Primary care office visit at a selected site based on preventative and outpatient CPT codes
 
• Have a PHQ-9 and an overall score <math>>10</math> or Question 9 <math>>0</math>
 

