## 5.2. Virtual Behavioral Health Integration

The flow of patients from initial contact to their follow-up calls is outlined in Appendix 1. In the existing VBHI primary care workflow, all patients are given the PHQ-2 survey. A score  $\geq 2$  triggers the PHQ-9 survey. The following day the behavioral health team receives a patient report. The report

includes patients seen the prior day at intervention sites that had an elevated PHQ-9 score >10 or reported suicide ideation (Question 9 >0). The Monday report includes patients seen Friday-Sunday. Patients associated with Medicare or other value-based insurance plan are identified in the report. The behavioral health care team will reach out to these patients for enrollment utilizing video assessment or telephonic outreach. The patient always has the option not to be followed by the behavioral health care team.

The behavioral health care team will complete the initial behavioral health assessment. The initial health assessment contains information such as preferred communication method, GAD-7, psychiatry provider, collateral resources, recent ED and hospital utilization, substance use disorder, medication barriers, appointment barriers, community resources, and crisis planning.

The frequency of follow-up assessments depends on the clinical presentation and medication recommendation and/or adherence. The assessment includes information such as a suicide ideation safety screening, an appointment reminder, appointment barrier evaluations, medication reconciliation, medication obtainment follow-up, substance use disorder follow-up, supportive listening, psychoeducation, community resource follow-up, and additional crisis planning.

The Columbia-Suicide Severity Rating Scale (C-SSRS) helps identify whether someone is at risk for suicide, and the severity and immediacy of the risk. It also identifies level of support the person needs. The screening tool is administered during each phone contact to measure suicide ideation. Follow-up patients enrolled in the VBHI program will receive follow-up phone calls. The frequency of calls is dependent on the clinical presentation and medication recommendation and/or adherence. A follow-up assessment is completed upon each phone call.

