### 5.3. Usual Care

All patients are given the PHQ-2 survey during the primary care visit. A score  $\geq 2$  triggers the PHQ-9 survey. The PHQ-9 offers providers a concise, self-administrated screening and diagnostic tool for Major Depressive Disorder (Table 1). Treatment can be based on the patients total PHQ-9 score. The patient's provider in the primary care practice has the option to refer the patient to community based behavioral health services, begin medication management within the primary care setting, or encourage the patient to obtain a psychiatric evaluation at the nearest emergency department to assess safety concerns including both suicidal and homicidal ideation. For patients that have a diagnosis of depression or dysthymia, the PHQ-9 is administered every 4 months. There are no follow-up behavioral health services based on the PHQ-9 score once the patient leaves the primary care practice.

PHQ-9 Score	Provisional Diagnosis	Treatment Recommendation
0-4	No Depression	None

5-9	Major Depression, mild	Reassurance and/or supportive counseling Education to call if deteriorates
10-14	Major Depression, moderate	Antidepressant and/or Psychotherapy
15-19	Major Depression, moderately severe	Antidepressant and/or Psychotherapy
≥20	Major Depression, severe	Antidepressant and Psychotherapy

Table 1.  
PHQ-9

scores and standard treatment recommendations

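### The exploratory model in section 6.2 names treatment and treatment-by-time effects that cannot be estimated in the stated population, which is VBHI enrollees only

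*Combined protocol and SAP*

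**What the plan says.** Section 6.2 (Statistical analysis) sets out a logit-link generalized linear mixed model for the exploratory outcomes at 3, 6, 9 and 12 months, with random effects for practice and patient. It then states: "Fixed effects will be the treatment group indicator, time indicator, and interaction between treatment group and time".

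Three places define who is analysed:
- Protocol Summary, Study Objectives: "Exploratory analyses among patients who enrolled in the VBHI program".
- Section 1.4: "patients who enrolled in the VBHI program in the first 9 months from study start".
- Section 5.1.2: "Symptom and health outcomes are assessed at 3, 6, 9, and 12-months among patients who enrolled in the VBHI program".

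Two places are less specific. The Study Procedures row of the Protocol Summary describes the 12-month exploratory follow-up without naming an arm. Section 6.2 applies intention-to-treat by site assignment to all analyses.

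On measurement, section 5.1.2 takes the anxiety baseline as "Pre- GAD-7 score from initial enrollment". Section 5.2 places that instrument with the VBHI team: "The initial health assessment contains information such as preferred communication method, GAD-7, psychiatry provider". Section 5.3 (Usual Care) mentions no GAD-7, and for the PHQ-9 says: "For patients that have a diagnosis of depression or dysthymia, the PHQ-9 is administered every 4 months".

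**The concern.** The model is written for two groups and the population for one. If every analysed patient is a VBHI enrollee, the model's two treatment terms have nothing to compare. The analyst would then have to drop terms or change the population after the data are in hand.

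What can be reported is change over time in people who took up the programme; section 5.2 notes "The patient always has the option not to be followed by the behavioral health care team". Most were also selected on a high baseline value. Entry needs a PHQ-9 total above 10 or a positive Question 9, and BMI, HbA1c and LDL have their own entry thresholds. Regression to the mean and natural recovery would therefore look like improvement. Section 11 plans a final report of all findings and a manuscript, and the plan carries no caution that these changes are not a programme effect.

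**Working it through.** The plan states no sample size, power or effect figure for this analysis, so there is no figure to reproduce. The question is whether the named effects are estimable.

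**Inputs.** Fixed effects: treatment, time and their interaction (section 6.2). Time points: 3, 6, 9 and 12 months (sections 1.4, 5.1.2 and 6.2). Population: VBHI enrollees (Protocol Summary, sections 1.4 and 5.1.2).

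**Columns.** With month 3 as reference: 1 intercept + 1 treatment + 3 time + 3 interaction = 8.

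**Both arms present.** 2 arms × 4 times = 8 distinct rows; rank 8 of 8.

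**Enrollees only.** Treatment equals 1 for everyone, which leaves 4 distinct rows (intercept, treatment | time 6, 9, 12 | interaction 6, 9, 12):
- month 3: 1, 1 | 0, 0, 0 | 0, 0, 0
- month 6: 1, 1 | 1, 0, 0 | 1, 0, 0
- month 9: 1, 1 | 0, 1, 0 | 0, 1, 0
- month 12: 1, 1 | 0, 0, 1 | 0, 0, 1

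The treatment column equals the intercept, and each interaction column equals its time column. The rank is 4, so 8 − 4 = 4 columns are redundant.

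**What is identified.** Only the sums (intercept + treatment) and (time + interaction at each of months 6, 9 and 12).
- VBHI minus usual care at month 3 is the treatment coefficient; at a later month it is treatment plus that month's interaction. Estimable: 0 of 4.
- Interaction contrasts: 0 of 3.
- Within-VBHI change, months 6, 9 and 12 against month 3 (time + interaction): 3 of 3.

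**Other codings of time.** With baseline as a fifth time level, the rank is 5 of 10 columns; with linear time, 2 of 4. Random effects for practice and patient do not change this.

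**After deleting the treatment terms.** Intercept plus time has full rank: 4 of 4, 5 of 5 and 2 of 2 under the three codings. Because 4 is also the rank of the 8-column model, the two models span the same space and give the same within-VBHI time estimates.

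**Outcome definitions that the corrected model must handle.**
- Anxiety: the Protocol Summary gives no baseline threshold; section 1.4 restricts to an initial GAD-7 above 10.
- Remission and suicidal ideation: the Protocol Summary and section 1.4 tie both to graduation, which under section 5.4 can fall at any time, yet also place assessment at the four fixed months. A value read once at graduation does not supply repeated measures.
- BMI, HbA1c and LDL: section 6.2 makes the dependent variable binary, but no yes/no cut-off for reduction is given.

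**The case against.** The strongest reply is that two arms were intended. The model names a treatment group, section 6.2 puts all analyses under intention-to-treat, and the Study Procedures row names no arm. On that reading the model is right and the population statements are wrong. This is possible, but intention-to-treat says how included patients are classified, not who is included, and none of these places says that usual-care patients enter this analysis. Three explicit statements say enrollees. Graduation, used for two outcomes, exists only within VBHI. Even on the two-arm reading, the sections conflict and must be reconciled.

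A second reply is that little changes: the time estimates are the same, most symptom outcomes are worded as percentages of patients, and the plan makes no explicit causal claim. The first part stands and limits the point. The last part is weakened because the named treatment terms themselves announce a comparison.

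A reader might go further and infer that no two-arm comparison could be made even if usual-care patients were added. The documents do not support that. Eligibility requires a PHQ-9 in both arms, usual care repeats it for diagnosed patients, and PHQ-9 scores at other visits may exist. Baseline BMI, HbA1c and LDL come from the primary care visit, and section 6 allows retrospective retrieval in either arm. Which contrasts could then be estimated would depend on an assumed schedule, visit window and time coding, so no count is given here. What the documents do show is that no usual-care GAD-7 and no usual-care PHQ-9 at 3, 6, 9 and 12 months is planned.

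**Conclusion.** The point holds. In the population stated in three places, no between-group or treatment-by-time effect in the exploratory model can be estimated (rank 4 of 8; 0 of 4 and 0 of 3 contrasts). What remains is uncontrolled change within self-selected enrollees.

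This assumes that all analysed enrollees carry the VBHI label. A patient first seen at a control practice who later enrolled elsewhere could keep a usual-care label under intention-to-treat, but the plan describes no such comparison and it would not be a randomised contrast. No size is put on regression to the mean, because the documents give no means, standard deviations or correlations.

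A reader might infer that the trial's main results are compromised. They are not: the primary and secondary models compare the two arms by site assignment and are untouched. The plan should be corrected before analysis because the error changes what the exploratory results can be said to show.

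**What to change.** Reconcile the Protocol Summary (Study Objectives and Study Procedures) and sections 1.4, 5.1.2 and 6.2 on the exploratory population. The choice is the sponsor's.

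- **If enrollees only:** in section 6.2 delete the treatment and interaction terms. Keep time as the fixed effect, with practice and patient random effects, for outcomes measured at 3, 6, 9 and 12 months. State that the results are uncontrolled changes in self-selected enrollees and that no VBHI effect is inferred.
- **If two arms:** correct the three population statements. Define the intervention group by site assignment rather than by enrolment, since restricting one arm to enrollees would lose the comparability that randomization gives. Limit the comparison to outcomes and times measured in both arms.

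In either case:
- Give one GAD-7 denominator.
- Say whether remission and suicidal ideation are read at graduation or at the fixed months; if at graduation, summarise each as a single proportion.
- For BMI, HbA1c and LDL, either define a yes/no cut-off for the logit model or report mean change from a linear mixed model.

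The enrollee-only route costs wording and a few outcome decisions, with no new data. The two-arm route also needs usual-care records to be retrieved, and the documents do not show how complete these would be.
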